7.1 Study flow and visit schedule

Table 7-1 Visit evaluation schedule

	Screening / Baseline	RT Day 22	RT Day 43	Post RT day 15	Post RT day 22	Post RT week 6	Post RT week 14	Post RT week 26
Visit no.	1	2	3	4	5	6	7	8
Treatment days*	-21 to -1							
Demography/informed consent (D)	X							
Inclusion/exclusion criteria (D)	X							
Relevant medical history/current medical conditions (D)	X							
Diagnosis and extent of cancer (D)	X							
Prior/post antineoplastic therapy (D)	X							
HIV history (S)	X							
Vital signs (D)	X	X	X	X	X	X	X	X
Height (D)	X							
Weight (D)	X	X	X	X	X	X	X	X
Physical examination (S)	X	X	X	X	X	X	X	X
ECOG performance status (D)	X	X			X	X	X	X
EKG ¹ (D)			X					
Correlative studies	X	X	X	X	X	X	X	X
Hematology ² (D)	X		X	X	X			
Coagulation (D)	X		X	X	X			
Biochemistry ³ (D)	X		X	X	X			
Serum Lipid Profile ⁴ (D)	X		X	X	X			
Prior/concomitant medications (D)	X			X	X			

	Screening / Baseline	RT Day 22	RT Day 43	Post RT day 15	Post RT day 22	Post RT week 6	Post RT week 14	Post RT week 26
Visit no.	1	2	3	4	5	6	7	8
Treatment days*	-21 to -1							
Everolimus ⁵				X				
HBV-DNA, HBsAg, HBs Ab, HBc Ab, HCV-RNA-PCR ⁶ (D)	X							
HBV DNA, HCV RNA-PCR ⁷ (D)	X							

* (+/- 1 day for visits 2,3,4,5; +/- 1 week for visits 6,7,8)

1. Baseline ECG is a standard 12 lead and must be performed within 21 days of first dose for patients enrolled and may be repeated at the investigator's discretion if clinically indicated
2. Hematology tests include a complete blood count (CBC). A total white blood cell (WBC) with absolute differentials (including neutrophil count plus bands, lymphocyte, monocyte, eosinophil, basophil counts), red blood cells (RBC), hemoglobin (Hgb), and a platelet count.
3. Serum Chemistry must include: BUN or uric acid, creatinine, LDH, total protein, electrolytes (sodium, potassium and calcium), total bilirubin, GGT, albumin, alkaline phosphatase, AST/sGOT fasting glucose.
4. Serum fasting lipid profile must include: total cholesterol and triglycerides. Patients should be in fasting state.
5. Everolimus is taken once daily for a total of five days, with drug dispensed at Visit 4.
6. All patients should be screened for hepatitis risk factors and any past illnesses of hepatitis B and hepatitis C. It is highly recommended that patients positive HBV-DNA or HBsAg are treated prophylactically with an antiviral for 1-2 weeks prior to receiving study drug (see Section 6.7.3). The antiviral treatment should continue throughout the entire study period and for at least 4 weeks after the last dose of study drug. Patients with viral hepatitis C risk factors should be screened for HCV RNA-PCR.
7. Patients on antiviral prophylaxis treatment or positive HBV antibodies should be tested for HBV-DNA according to study visit schedule. Patients with positive HCV-RNA PCR or a history of past infection, even if treated and considered 'cured' – should be followed by HCV-RNA PCR according to visit

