4. Uncontrolled diabetes mellitus as defined by HbA1c $> 8\%$ despite adequate therapy. Patients with a known history of impaired fasting glucose or diabetes mellitus (DM) may be included, however blood glucose and antidiabetic treatment must be monitored closely throughout the trial and adjusted as necessary;
5. Patients who have any severe and/or uncontrolled medical conditions such as:
 - a. unstable angina pectoris, symptomatic congestive heart failure, myocardial infarction ≤ 6 months prior to start of Everolimus, serious uncontrolled cardiac arrhythmia, or any other clinically significant cardiac disease
 - b. Symptomatic congestive heart failure of New York heart Association Class III or IV
 - c. active (acute or chronic) or uncontrolled severe infection, liver disease such as cirrhosis, decompensated liver disease, and active and chronic hepatitis (i.e. quantifiable HBV-DNA and/or positive HbsAg, quantifiable HCV-RNA),
 - d. known severely impaired lung function (spirometry and DLCO 50% or less of normal and O₂ saturation 88% or less at rest on room air),
 - e. active, bleeding diathesis;

6. Chronic treatment with corticosteroids or other immunosuppressive agents. Topical or inhaled corticosteroids are allowed;
7. Known history of HIV seropositivity;
8. Patients who have received live attenuated vaccines within 1 week of start of Everolimus and during the study. Patient should also avoid close contact with others who have received live attenuated vaccines. Examples of live attenuated vaccines include intranasal influenza, measles, mumps, rubella, oral polio, BCG, yellow fever, varicella and TY21a typhoid vaccines;
9. Patients who have a history of another primary malignancy, with the exceptions of: non-melanoma skin cancer, and carcinoma in situ of the cervix, uteri, or breast from which the patient has been disease free for ≥ 3 years;
10. Patients with a history of non-compliance to medical regimens or who are considered potentially unreliable or will not be able to complete the entire study;
11. Patients who are currently part of or have participated in any clinical investigation with an investigational drug within 1 month prior to dosing;
12. Pregnant or nursing (lactating) women;

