The most common grade 3/4 ADRs, suspected to be related to treatment by the investigator (incidence $\geq 1/100$ to $<1/10$) were stomatitis, anemia, hyperglycemia, fatigue, infections, pneumonitis, diarrhea, asthenia, thrombocytopenia, neutropenia, dyspnea, lymphopenia, proteinuria, hemorrhage, hypophosphatemia, rash, hypertension, aspartate aminotransferase (AST) increased, alanine aminotransferase (ALT) increased, and pneumonia and diabetes mellitus.

The below table presents the frequency category of ADRs reported in the pooled safety analysis.

ADRs are listed according to MedDRA system organ class. Within each system organ class, the adverse reactions are ranked by frequency, with the most frequent reactions first. In addition, the corresponding frequency category using the following convention (CIOMS III) is also provided for each adverse reaction: very common ($\geq 1/10$); common ($\geq 1/100$ to $<1/10$); uncommon ($\geq 1/1,000$ to $<1/100$); rare ($\geq 1/10,000$ to $<1/1,000$); very rare ($<1/10,000$)

Infections and infestations

Very common - Infections^a

Blood and lymphatic system disorders

Very common	- Anemia,
Common	- Thrombocytopenia, neutropenia, leukopenia, lymphopenia
Uncommon	- Pancytopenia
Rare	- Pure red cell aplasia

Immune system disorders

Uncommon - Hypersensitivity

Metabolism and nutrition disorders

Very common - Decreased appetite, hyperglycemia, hypercholesterolemia
Common - Hypertriglyceridemia, hypophosphatemia, diabetes mellitus, hyperlipidemia, hypokalemia, dehydration

Psychiatric disorders

Common - Insomnia

Nervous system disorders

Very common - Dysgeusia, headache

Uncommon - Ageusia

Cardiac disorders

Uncommon - Congestive cardiac failure

Vascular disorders

Common - Hemorrhage^b, hypertension,

Uncommon - Deep vein thrombosis

Respiratory, thoracic and mediastinal disorders

Very common - Pneumonitis^c, epistaxis, cough,

Common - dyspnea

Uncommon - Hemoptysis, pulmonary embolism

Rare - , acute respiratory distress syndrome

Gastrointestinal disorders

Very common - Stomatitis^d, diarrhea, nausea

Common - Vomiting, dry mouth, abdominal pain, oral pain, dyspepsia, dysphagia

Skin and subcutaneous tissue disorders

Very common - Rash, pruritus

Common - Dry skin, nail disorder, acne, erythema, hand-foot syndrome

Rare - Angioedema

Musculoskeletal and connective tissue disorders

Common - Arthralgia

Renal and urinary disorders

Common - Proteinuria, Renal failure

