- Clinical chemistry: glucose (fasting) increased, phosphate decreased, potassium decreased, AST increased, ALT increased, creatinine increased cholesterol (total) increased, triglycerides increased, albumin decreased (all common).

Tuberous sclerosis complex (TSC)

The most frequent ADRs (incidence $\geq 1/10$ and suspected to be related to treatment by the investigator) from the pooled safety database are (in decreasing order): stomatitis, upper respiratory tract infections, amenorrhea, hypercholesterolemia, nasopharyngitis, acne, menstruation irregular, sinusitis, and pneumonia

The most frequent grade 3/4 adverse reactions (incidence $\geq 1/100$ to $< 1/10$ and suspected to be related to treatment by the investigator) were stomatitis, amenorrhea, pneumonia, neutropenia, pyrexia, and gastroenteritis viral.

The below table shows the incidence of ADRs based on pooled data in patients receiving everolimus in the TSC studies (including both the double-blind and open-label study and extension periods). ADRs are listed according to MedDRA system organ class. Frequency categories are defined using the following convention: very common ($\geq 1/10$); common ($\geq 1/100$ to $< 1/10$); uncommon ($\geq 1/1,000$ to $< 1/100$); rare ($\geq 1/10,000$ to $< 1/1,000$); very rare ($< 1/10,000$); not known (cannot be estimated from the available data). Within each frequency grouping, ADRs are presented in order of decreasing frequency.

Infections and infestations

Very common - Upper respiratory tract infection, nasopharyngitis, sinusitis, pneumonia

Common - Otitis media, urinary tract infection, pharyngitis, cellulitis,

pharyngitis streptococcal, gastroenteritis viral, , gingivitis

Uncommon - Herpes zoster, bronchitis viral

IRB NUMBER: PHXB-17-0072-70-15

IRB APPROVAL DATE: 07/03/2018

Blood and lymphatic system disorders

Common - Neutropenia, anemia, leukopenia, lymphopenia, thrombocytopenia

Immune system disorders

Uncommon - Hypersensitivity

Metabolism and nutrition disorders

Very common - Hypercholesterolemia

Common - Hyperlipidemia, decreased appetite, hypophosphatemia, hypertriglyceridemia

Psychiatric disorders

Common - Insomnia,

Uncommon - aggression

Nervous system disorders

Common - Headache, dysgeusia

Vascular disorders

Common - Hypertension, lymphedema

Respiratory, thoracic and mediastinal disorders

Common - Cough, epistaxis, Pneumonitis

Gastrointestinal disorders

Very common - Stomatitis^a

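### No serum phosphate is scheduled before or after dosing, although the protocol lists hypophosphatemia as a common grade 3/4 everolimus reaction that could count as a DLT

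*Protocol*

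**What the plan says.** **The panel.** Footnote 3 of Table 7-1 (section 7.1) reads "Serum Chemistry must include: BUN or uric acid, creatinine, LDH, total protein, electrolytes (sodium, potassium and calcium), total bilirubin, GGT, albumin, alkaline phosphatase" and ends with "AST/sGOT fasting glucose". The electrolytes it requires are only those in "electrolytes (sodium, potassium and calcium". Phosphate is not named there, in the lipid footnote or in any row of the table. Chemistry is drawn at Visits 1, 3, 4 and 5. On dosing, footnote 5 says "Everolimus is taken once daily for a total of five days, with drug dispensed at Visit 4", so Visit 5 (post-RT day 22) is the only scheduled chemistry after treatment.

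**The known reaction.** Section 6.2.2 names phosphate among the laboratory values most often lowered. Section 8.1.1 gives the most common grade 3/4 reactions in the oncology pool, with incidence from 1/100 to below 1/10; the list contains "proteinuria, hemorrhage, hypophosphatemia, rash, hypertension". Its list of grade 3/4 chemistry abnormalities, all classed as common, begins "glucose (fasting) increased, phosphate decreased, potassium decreased, AST increased". The tuberous sclerosis pool in the same section also classes grade 3/4 phosphate decrease as common.

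**The decision rule.** Sections 4.1, 6.1 and 9.1 define a DLT as an adverse event of grade 3 or higher related to everolimus, with no exemption for phosphate. No DLT among the first 3 patients at 5 mg leads to 10 mg. One DLT leads to 3 more patients, and no further DLT among those also leads to 10 mg.

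**When a laboratory value counts.** Under sections 8.1.1 and 8.1.2 an abnormal value is an adverse event only if it causes signs or symptoms, is judged clinically significant, needs therapy or needs a change in study medication.

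**The concern.** The initial objective in section 3 is to document the safe dose, and the only tool for this is a count of DLTs in very few patients. That count depends on what is measured. Low phosphate can be silent, and no other analyte in the panel stands in for it. A patient whose phosphate fell far enough to need therapy would meet the adverse event rule, but without a test nobody would know that therapy was needed.

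A baseline is missing as well. The glossary takes the safety baseline as the last value on or before the start of study treatment. If phosphate is never scheduled, that value may not exist. A low result found by chance after dosing would then be hard to attribute, since these patients have just finished RT or chemoRT and may be eating poorly. Relatedness is part of the DLT definition, so the gap affects classification as well as detection.

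**Working it through.** **The plan's own figures.** Section 9.1 gives a standard error of 0.32 of the standard deviation for 10 patients: 1/√10 = 0.316, which agrees. The trial totals also agree: 3 + 10 = 13, 6 + 10 = 16, and 10. None of these bears on DLT detection, for which the protocol gives no figure.

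**Coverage of the listed abnormalities.** Section 8.1.1 names nine grade 3/4 chemistry abnormalities in the oncology pool.

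| Abnormality | Required by Table 7-1 |
|---|---|
| Glucose | yes (footnote 3) |
| Phosphate | no |
| Potassium | yes (footnote 3) |
| AST | yes (footnote 3) |
| ALT | no (AST is a partial companion) |
| Creatinine | yes (footnote 3) |
| Cholesterol | yes (footnote 4) |
| Triglycerides | yes (footnote 4) |
| Albumin | yes (footnote 3) |

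Seven of nine are covered. Phosphate is missing and has no companion test, which looks more like an oversight than a choice.

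**Chance of at least one case in the patients who decide escalation.** Inputs: rate h from 1% to 10% (the band in section 8.1.1; 10% is its excluded upper limit), and n = 3, or 6 if the cohort is expanded (section 4.1). The formula is 1 − (1 − h)^n.

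| h | n = 3 | n = 6 |
|---|---|---|
| 1% | 1 − 0.99³ = 3.0% | 1 − 0.99⁶ = 5.9% |
| 5% | 1 − 0.95³ = 14.3% | 1 − 0.95⁶ = 26.5% |
| 10% (limit) | 1 − 0.90³ = 27.1% | 1 − 0.90⁶ = 46.9% |

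**Effect on the decision.** For a per-patient DLT probability p, the stated rule reaches 10 mg with probability (1 − p)³ + 3p(1 − p)²(1 − p)³. Assume, for illustration only, that all other DLTs occur at 10% and independently of phosphate. The combined probability is then p = 1 − 0.90 × (1 − h).

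- Phosphate never seen: p = 0.10, and 0.729 + 0.177 = 90.6%.
- Every case seen and counted, h = 1%: p = 0.109, giving 89.1%.
- Every case seen and counted, h = 10%: p = 0.19, giving 73.0%.

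If there were no other DLTs, the figure is 100% unseen, against 99.9% (h = 1%) to 90.6% (h = 10%) seen. The seen figures treat every grade 3/4 value as a related adverse event, so the differences are upper bounds for the assumed rates.

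**The case against.** The strongest reply has four parts.

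1. **The panel is a minimum.** A site may add phosphate, a symptomatic patient may be tested, and section 8 accepts adverse events found by any means. This stands. A reader might infer that the escalation decision has no sight of low phosphate and that such a case is barred from the DLT count. The text does not support that: what is missing is a scheduled measurement.

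2. **Many low values would not be DLTs.** Under the adverse event rule a silent value judged not clinically significant, needing no therapy and no change in study medication, is not reported, so measuring it would change nothing. This also stands, and it narrows the point to cases that would meet the rule if seen. Those remain, because section 8.1.1 lists hypophosphatemia as an adverse reaction in its own right and not only as a laboratory finding.

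3. **The rate is borrowed.** The band describes pooled oncology use. The deciding patients take 5 mg for 5 days, and section 4.1 expects the known toxicities not to develop. The figures are therefore illustrations under an assumption.

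4. **No rule depends on phosphate.** The protocol has no phosphate eligibility limit or stopping rule for the missing test to defeat, and proteinuria, in the same reaction list, has no row in Table 7-1 either. So this is a gap in safety measurement and not an internal contradiction. It is still worth closing, because the blood is already drawn.

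Three further inferences do not hold. Taking 13 treated patients as the base gives 12% to 75% (1 − 0.99¹³ to 1 − 0.90¹³), but 10 of those 13 are treated after 10 mg has been opened. The position of phosphate next to glucose is not a ranking: the grade 3/4 chemistry list states no order, and in the any-grade list that is in decreasing order phosphate is fifth. Finally, exclusion 4 begins "Uncontrolled diabetes mellitus as defined by HbA1c" while Table 7-1 has no HbA1c row. But section 5.1 already requires baseline results showing that every criterion is met, so that exclusion can be applied without a separate row.

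**Conclusion.** The point holds as a modest gap in safety measurement. The schedule requires no phosphate value before or after dosing, while the protocol itself calls a grade 3/4 fall in phosphate common. A case without symptoms that would need therapy could be left out of the count that opens 10 mg.

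For the first 3 patients the chance of at least one grade 3/4 case runs from about 3% to just under 27%; for 6 patients it runs from about 6% to just under 47%. This rests on three assumptions: that the pooled oncology band applies to this trial, that patients are independent, and that every grade 3/4 case is counted. The first may be too pessimistic for a 5-day course, and the third overstates what would qualify as an adverse event. At the low end of the band the effect on escalation is negligible; near the top it would be noticeable. The case for the change rests on its low cost rather than on a large expected effect.

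**What to change.** Add serum phosphate to the footnote 3 panel at the visits where chemistry is already taken (Visits 1, 3, 4 and 5). This gives a pre-dose value for judging relatedness and a post-dose value at Visit 5 for the DLT count. The DLT definition and the adverse event rule need no change.

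The cost is one more analyte on blood already drawn, with no added visit. It is more than a wording change, because section 10 lists the addition of a safety-monitoring test among the amendments that need IRB approval at each center.

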5.1 Inclusion and Exclusion criteria

Patients must have baseline evaluations performed prior to the first dose of study drug and must meet all inclusion and exclusion criteria. Results of all baseline evaluations, which assure that all inclusion and exclusion criteria have been satisfied, must be reviewed by the Principal Investigator or his/her designee prior to enrollment of that patient. In addition, the patient must be thoroughly informed about all aspects of the study, including the study visit schedule and required evaluations and all regulatory requirements for informed consent. The written informed consent must be obtained from the patient prior to enrollment. The following criteria apply to all patients enrolled onto the study unless otherwise specified.

Inclusion criteria:

1. Age 18-75 years
2. Performance status ECOG ≤ 2
3. Adequate bone marrow function as shown by: ANC $\geq 1.5 \times 10^9/L$, Platelets $\geq 100 \times 10^9/L$, Hgb $> 9 \text{ g/dL}$;
4. Adequate liver function as shown by:
 - a. Total serum bilirubin $\leq 2.0 \text{ mg/dL}$,
 - b. ALT and AST $\leq 2.5 \times \text{ULN}$ ($\leq 5 \times \text{ULN}$ in patients with liver metastases),
 - c. INR ≤ 2 ;
5. Adequate renal function: serum creatinine $\leq 1.5 \times \text{ULN}$;
6. Fasting serum cholesterol $\leq 300 \text{ mg/dL}$ OR $\leq 7.75 \text{ mmol/L}$ AND fasting triglycerides $\leq 2.5 \times \text{ULN}$. NOTE: In case one or both of these thresholds are exceeded, the patient can only be included after initiation of appropriate lipid lowering medication;
7. Signed informed consent obtained prior to any screening procedures.
8. Patients with locally advanced squamous cell carcinoma of the head and neck, treated with curative intent either in the post-operative or definitive setting with high dose radiotherapy ($\geq 50 \text{ Gy}$) with or without chemotherapy.

Exclusion criteria:

1. Patients currently receiving anticancer therapies or who have received anticancer therapies within 2 weeks of the start of Everolimus (including chemotherapy, radiation therapy, antibody based therapy, etc.);
2. Known intolerance or hypersensitivity to Everolimus or other rapamycin analogs (e.g. sirolimus, temsirolimus);
3. Known impairment of gastrointestinal (GI) function or GI disease that may significantly alter the absorption of oral Everolimus;

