6.2.1.2 Dosing modifications

For patients who do not tolerate the protocol-specified dosing schedule, dose adjustments are not permitted.

Table 6-1 and Table 6-2 list the dosing guidelines for Everolimus-related non-hematologic and hematologic toxicities.

Management of severe or intolerable adverse drug reactions (ADRs) may require temporary dose interruption of Afinitor therapy.

The proceeding sections summarize recommendations for dose interruption, or discontinuation of Afinitor in the management of ADRs. General management recommendations are also provided as applicable. Clinical judgment of the treating physician should guide the management plan of each patient based on individual benefit/risk assessment.

Table 6-1 Dosing guidelines for Everolimus-related non-hematologic toxicities

Toxicity	Action
Non-Infectious Pneumonitis	Discontinue Everolimus.
Reactivation of HBV or HCV flare	Discontinue Everolimus.
AST or ALT elevation Grade 1 ($>$ ULN - 3.0 x ULN)	Maintain current dose level
Grade 2 ($>$ 3.0 - 5.0 x ULN)	
AST or ALT elevation Grade 3 ($>$ 5.0 - 20.0 ULN)*	Discontinue Everolimus
AST or ALT elevation Grade 4 ($>$ 20 x ULN)*	Discontinue Everolimus
Intolerable grade 2 mucositis, or grade 3 AE, except hyperglycemia or hypertriglyceridemia or hypercholesterolemia (see Section 6.2.3.8)	Discontinue Everolimus
Any other grade 4	Discontinue Everolimus
Grade 3 or 4 clinical liver failure (asterixis or encephalopathy/coma)	Discontinue Everolimus

* Should HCV flare be confirmed, the guidelines for flare must take precedence (Table 6-6)

Table 6-2 Dosing guidelines for Everolimus-related hematologic toxicities

Toxicity	Action
Grade 2 thrombocytopenia (platelets $<$ 75, \geq 50 x10 ⁹ /L)	No action
Grade 3 thrombocytopenia (platelets $<$ 50, \geq 25 x10 ⁹ /L)	Discontinue Everolimus
Grade 4 thrombocytopenia (platelets $<$ 25 x10 ⁹ /L)	Discontinue Everolimus
Grade 3 neutropenia or anemia (neutrophil $<$ 1, \geq 0.5 x10 ⁹ /L)	Discontinue Everolimus
Grade 4 neutropenia or anemia	Discontinue Everolimus
Febrile neutropenia	Discontinue Everolimus

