* All reactivations of HBV are to be recorded as grade 3 (e.g. CTCAE Version 3.0 - Investigations/Other: Viral Reactivation), unless considered life threatening by the investigator, in which case they should be recorded as grade 4. Date of viral reactivation is the date on which the rise or reappearance of HBV-DNA was recorded.

Monitoring for hepatitis C flare

The following two categories of patients should be monitored every 4–8 weeks for HCV flare:

- Patients with detectable HCV RNA-PCR test at screening.
- Patients known to have a history of HCV infection, despite a negative viral load test at screening (including those that were treated and are considered ‘cured’)

For definitions of HCV flare and actions to be taken in the event of a flare, please refer to Table 6-6.

Table 6-6 Guidelines for the management of hepatitis C flare

Baseline results	HCV flare definition*	HCV flare management
Detectable HCV-RNA	> 2 log ₁₀ IU/mL increase in HCV-RNA AND ALT elevation > 5 x ULN or 3 x baseline level, whichever is higher.	Discontinue Everolimus
Knowledge of past hepatitis C infection with no detectable HCV-RNA	New appearance of detectable HCV-RNA AND ALT elevation > 5 x ULN or 3 x baseline level, whichever is higher.	Discontinue Everolimus

* All flares of HCV are to be recorded as grade 3 (e.g. CTCAE Version 3.0 - Investigations - Other: Viral Flare), unless considered life threatening by the investigator; in which case they should be recorded as grade 4. Date of viral flare is the date on which both the clinical criteria described above were met. (e.g., for a patient whose HCV-RNA increased by 2 logs on 01 JAN 2011 and whose ALT reached $> 5 \times$ ULN on 22 JAN 2011, the date of viral flare is 22 JAN 2011).

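### The required chemistry panel names AST but not ALT, so an ALT-only grade 3 rise after everolimus could be missed and the DLT count can only err downward

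*Protocol*

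**What the plan says.** Footnote 3 to Table 7-1 (Protocol section 7.1) begins "Serum Chemistry must include: BUN or uric acid, creatinine, LDH, total protein" and, after the electrolytes, bilirubin, GGT and albumin, ends "alkaline phosphatase, AST/sGOT fasting glucose". AST is named and ALT is not. No other row or footnote of the table adds it. Biochemistry is ticked at Visits 1, 3, 4 and 5: screening, RT day 43, post-RT day 15 and post-RT day 22.

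ALT is used elsewhere in the Protocol:

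- **Section 5.1, inclusion criterion 4b** sets an upper limit on ALT as well as AST.
- **Section 6.2.1.2, Table 6-1** assigns an action to each grade of transaminase rise. The row "AST or ALT elevation Grade 3" and the grade 4 row below it carry discontinuation.
- **Section 6.2.2.10, Table 6-6** requires, in both rows of the hepatitis C flare definition, "ALT elevation > 5 x ULN or 3 x baseline level, whichever is higher" together with a viral RNA criterion. Flares are recorded as grade 3 or 4.
- **Section 8.1.1** lists "alanine aminotransferase (ALT) increased" among the most common grade 3/4 reactions suspected to be drug-related.

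Sections 4.1, 6.1 and 9.1 define a dose-limiting toxicity (DLT) as an adverse event of at least grade 3 attributed to everolimus. The DLT count in the first 3 patients, or the first 6, decides whether the dose goes from 5 mg to 10 mg.

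**The concern.** The rules call for a measurement that the visit schedule does not require. The gap matters most around dosing. Visit 5 is the only scheduled chemistry after everolimus starts, so an ALT not drawn then is not recovered at a later scheduled draw. Visit 4 would supply the pre-dose value needed to judge whether a later rise is due to everolimus or to the preceding radiotherapy or chemoradiotherapy.

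At stake is the completeness of the DLT count. With cohorts of 3 or 6, a single unrecorded event can change the next step from expanding the cohort to escalating. The error runs in one direction: leaving ALT out can hide a DLT but cannot create one. With two sites enrolling, sites may also differ in whether they run ALT by habit.

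**Working it through.** The Protocol states no figure on this point that could be reproduced, so the check is a comparison of the text followed by a bound on size.

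**1. Requirement against schedule**

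| Where ALT is needed | When | Does the Protocol require ALT then? |
|---|---|---|
| Criterion 4b | Screening | Yes, implied by the criterion itself |
| Pre-dose reference for attribution | Visit 4 | No |
| DLT ascertainment after dosing | Visit 5 | No |
| Table 6-6 flare checks, every 4 to 8 weeks | Partly after Visit 5 | No chemistry is scheduled |

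**2. Age of the screening ALT at dosing.** Screening precedes radiotherapy. RT day 43 marks about six weeks and post-RT day 15 about two more, so a screening ALT is at least about 6 + 2 = 8 weeks old at the first dose.

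**3. Position of Visit 5.** Visits 4 and 5 each have a window of ±1 day. If dosing starts on the day of Visit 4, at the latest post-RT day 16, the fifth daily dose falls on day 16 + 4 = 20. The earliest Visit 5 is day 22 − 1 = 21. Visit 5 therefore follows an uninterrupted course even at the extremes of the windows. It bears on counting DLTs, not on stopping treatment during the course.

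**4. Flare checks.** If the interval is counted from a first dose on post-RT day 15 (an assumption; the origin is not stated), the first check falls between day 15 + 28 = 43 and day 15 + 56 = 71. The last scheduled chemistry is on day 22.

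**5. Upper bound on the event.** For a per-patient rate p, the chance of at least one grade 3/4 ALT event in three patients is 1 − (1 − p)³. The Protocol gives two frequency categories in section 8.1.1.

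- Oncology pool, common (1% to under 10%): 1 − 0.99³ = 0.030 and 1 − 0.90³ = 0.271, so 3% to 27%.
- Tuberous sclerosis pool, uncommon (0.1% to under 1%): 1 − 0.999³ = 0.003 and 1 − 0.99³ = 0.030, so about 0.3% to 3%.

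Both count every grade 3/4 ALT event, including those that AST would also show.

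**6. Effect on escalation, on assumed rates.** Escalation follows 0 DLTs in 3, or 1 in 3 and then 0 in the next 3:

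P(escalate) = (1 − p)³ + 3p(1 − p)² × (1 − p)³

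Assume 5% of patients have some other DLT, independent of ALT.

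- ALT-only events unseen, p = 0.05: 0.857 + 0.135 × 0.857 = 0.973.
- ALT-only events seen, at an assumed rate of 2%, 5% or 10%: p = 1 − 0.95 × 0.98 = 0.069, 1 − 0.95 × 0.95 = 0.0975, or 1 − 0.95 × 0.90 = 0.145. P(escalate) is then 0.952, 0.910 or 0.824.

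The Protocol gives no DLT rate and no ALT-only rate. These values show direction and scale only.

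**The case against.** The opposing case is substantial, and most of it limits the point without removing it.

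- **The list is a minimum.** A reader might infer that it is closed and that the ALT rules cannot be applied at all. The text does not support that: sites may add tests, and criterion 4b already implies ALT at screening. It remains true that nothing requires ALT at Visits 4 and 5.
- **AST is measured.** A reader might infer that the discontinuation rule is inoperable. Table 6-1 acts on either enzyme, so AST still drives it. Only an ALT rise without a matching AST rise is lost.
- **Stopping during the course.** No chemistry is scheduled between Visits 4 and 5, so adding ALT would not make the rule work while the tablets are being taken. That stands. The gain is in DLT ascertainment.
- **Not every ALT rise is a DLT.** Under sections 8.1.1 and 8.1.2 a laboratory abnormality becomes an adverse event only if it is symptomatic, clinically significant, or needs therapy or a change of study medication. After a completed course the last route has gone, so a Visit 5 rise must qualify by another. It must also be attributed to everolimus.
- **One DLT does not block escalation.** In the first three patients it adds three more.
- **The hepatitis C route is narrow.** Quantifiable HCV-RNA is an exclusion, which leaves mainly patients with past infection.
- **A word may have been lost.** A separator is missing between AST/sGOT and fasting glucose, so a dropped item is plausible, either in drafting or in conversion from PDF. The source page must be checked first.

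**Conclusion.** The point stands as an internal inconsistency of modest size. As the text reads, the schedule requires AST but not ALT at the pre-dose and post-dose draws, while the eligibility, toxicity-action and flare rules rely on ALT. Any grade 3 or higher ALT event lost in this way lowers the DLT count and favours escalation.

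The size cannot be fixed from the Protocol. It is tempting to read 3% to 27% as the chance of an unseen DLT in the first cohort. It is instead the chance of any grade 3/4 ALT event at the oncology-pool rates. The tuberous sclerosis pool gives about 0.3% to 3%. The oncology pool is the closer population, but both ranges are upper bounds because of overlap with AST and a five-day exposure. The conclusion assumes that footnote 3 is complete as printed and that the biochemistry ticks sit under Visits 1, 3, 4 and 5, as the extracted table shows.

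**What to change.** Check the source page for a word lost from footnote 3. If ALT is absent there too:

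1. Add ALT/sGPT to footnote 3, so that it is measured at the chemistry visits already ticked (Visits 1, 3, 4 and 5).
2. Reconcile footnote 3 and the visit schedule with criterion 4b, Table 6-1 and Table 6-6. This includes the 4-to-8-week hepatitis C flare monitoring, which runs beyond the last scheduled chemistry and which step 1 alone would not serve.

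Step 1 costs one analyte in blood draws already planned and changes no dose or clinical rule. Step 2 is mainly an edit to the text. How the later flare checks obtain their ALT is for the investigator and sponsor to settle.
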